### **5.1 Inclusion /Exclusion Criteria**

#### **Inclusion:**

- Subjects between the ages of 11 and 17 undergoing arthroscopic knee surgery.
- Able to independently complete the VAS pain scales.
- Subjects who are neurologically intact at area of injection.
- English speaking.

#### **Exclusion:**

- Subjects with known allergies to lidocaine.
- Presence of developmental delay.
- Subjects with blood disorders affecting coagulation.
- Subjects on blood thinners.
- Subjects receiving chemotherapeutic agents.
- Those who use or receive analgesia prior to procedure, except for acetaminophen or NSAIDs.
- Any other local sedation at the area of nerve block injection.
- \*Non-English Speaking
- Subjects with signs of skin infection or pathology at the injection site.

\*The consent form and other documents for this study are not available in any other language. Non-English speaking families may not fully understand the study.

## **6. Study Duration/ Study Timeline:**

Stage 1, enrollment of patients: 12 to 24 months.

Stage 2, data collection and data analysis: 3-6 months.

Stage 3, presentation and publication: 6-12 months.

Goal is to conclude data analysis by: September 2017

## **7. Statistical Analysis Plan:**

Analyses will vary by specific aim. To evaluate our hypotheses, we will use exact and non-parametric hypothesis testing procedures. Confidence intervals (95%) of differences will be computed. Regression analysis will be employed when adjustment between comparison groups is considered necessary.

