### **1.6 Primary Objective**

The primary objective is to measure the change in pain from a femoral or sciatic nerve block with the use of J-tip injected lidocaine compared to needle injected lidocaine for local anesthesia prior to the regional nerve block.

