### **1.7 Secondary Objectives**

- To evaluate the difference in pain from local anesthetic infiltration with J-tip needless injection compared to needle injection.
- To evaluate efficacy of femoral and/or sciatic nerve block after J-tip lidocaine injection compared to needle injected lidocaine post operatively by tracking pain levels to post operative day three.
- To assess patient and parent satisfaction with J-tip use.
- To assess changes in post operative pain medication amounts with J-tip use.
- To evaluate changes in post operative nausea and/or vomiting with J-tip use.
- To evaluate changes in post operative anti-nausea/anti-emetic medication use with J-tip use.
- To evaluate changes in time of PACU stay.

- To assess any differences in outcomes or pain after J-tip or needle injected lidocaine with respect to BMI, thigh circumference, gender, ethnicity or operative time in pain reporting measures, satisfaction or medication usage.

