#### **3.2 Secondary Objectives**

- To evaluate the difference in pain from local anesthetic infiltration with J-tip needleless injection compared to needle injection by use of VAS.
- To evaluate efficacy of femoral nerve block after J-tip lidocaine injection post operatively by use of VAS.
- To assess patient and parent satisfaction with J-tip use by satisfaction questionnaire.
- To assess changes in post operative pain medication amounts with J-tip use.
  - 1) Type and amount in PACU
  - 2) Home log of amount taken daily for post operative days one through three (Standard opiate based pain medication prescription given to each patient). Measured in number of pills/tablets taken each day.
- To evaluate changes in post operative nausea and/or vomiting with J-tip use.
  - Calculated as “Present” or “Absent”
- To evaluate changes in post operative anti-nausea/anti-emetic medication use with J-tip use.
  - 1) Type and amount in PACU

- 2) Home record log of amount taken daily (Standard medication prescription given to each patient). Measured in number of pills/tablets taken each day.
- To evaluate time in PACU with use of J-tip compared to needle use group prior to regional block. PACU stay time recorded in minutes.

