Times will be recorded for; time of J-tip administration, time of regional block performance, operating room arrival time, incision time, surgical end time, PACU arrival time and PACU discharge time. The amount of time from regional block to arrival in operating room and to incision time will be calculated. The surgical procedure time and amount of time in PACU will also be calculated.

Visual analogue pain scales will be completed prior to and immediately after J-tip use or needle local anesthesia infiltration. The scale immediately after will be with regard to pain felt at time of J-tip use or needle introduction. The scale will be completed once again prior to and immediately after needle introduction for each regional blockade. The scale immediately after will be with regard to pain felt at time of regional block needle introduction. Visual analogue pain scale will be recorded in PACU. All scoring will be performed on separate VAS assessments without patient access to previous scores.

The patient will record visual analogue pain scales on post-operative days one through three. The anesthesiologist will collect telephone verbal pain scores on a 0-10 scale on post-operative days one and two. This is current standard procedure for all patients who

receive a regional block. The femoral nerve block catheter, when utilized, is left in place for 40 hours from the initial femoral nerve block procedure. The number of days until the post-operative visit will be recorded. Another visual analogue pain scale will be completed at the first post-operative visit. An Arthroscopic Surgery Satisfaction Questionnaire will be completed by the patient and a parent or guardian at the first post-operative visit. The questionnaire will be specific to the patient's randomized treatment group. If the patient was randomized to receive the J-Tip, the patient and parent will receive the J-Tip questionnaire and if the patient was randomized to receive the traditional needle and syringe, the patient and parent will receive the needled syringe questionnaire. The sex of the parent or guardian completing the form will be recorded.

It will also be recorded if intra-articular analgesic injection is given intra-operatively. The amount and type of pain and anti-nausea/emeitic and pain medication use will be recorded in PACU and by the patient on the first three post-operative days.

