No statistical significance when comparing means Injection Type the following variables: 1st Type of Sedation, 1st Total Quantity of sedation used (mg), 2nd Type of Sedation Used, Total Quantity 2nd Type of sedation used (mcg), 3rd Type of Sedation Used, Total Quantity 3rd Type of sedation used (mcg), Visual Analog Scale (VAS) prior to local femoral, VAS prior to femoral, VAS immediately after femoral, VAS prior to local sciatic, VAS prior to sciatic, VAS immediately after sciatic, VAS prior to PACU Discharge.

VAS Immediately After Local Femoral:

Ordinary Least Squares Regression is utilized to determine if the Visual Analog Scale (VAS) immediately after local femoral for Needle Injections is significantly different from J-Tip Injections. This regression is run to determine if the injection type can statistically predict VAS immediately after local femoral. There is an independence of residuals, as assessed by a Durbin-Watson statistic, of 1.688 (Table 4). The assumptions of linearity, independence of errors, homoscedasticity, unusual points, and normality of residuals were met. The model is statistically significant,  $F (6, 100) = 10.215, p \leq .001$ , adj.  $R^2 = .343$ . Injection type statistically significantly predicts VAS immediately after local femoral, as seen in Table 3,  $\beta = -2.020, t = -6.266, p \leq .001$ . The beta explains that if a J-tip injection was given it would decrease the VAS immediately after local femoral by approximately 2. Regression coefficients and standard errors can be found in Appendix.

Variable	Adjusted R 	Model			Injection Type		
		df	F	Sig.	Beta	T	Sig.
VAS Immediately After Local Femoral	.343	6	10.215	.000	-2.020	-6.266	.000

Table 3: Beta Explanation for VAS Immediately After Local Femoral

Model	R	R 	Adjusted R 	Standard Error of the Estimate	Durbin-Watson
1	.616 a	.380	.343	1.656	1.688

- Predictors: (Constant), Thigh Circumference (cm), Ethnicity, Injection Type, Age, Gender BMI
- Dependent Variable: VAS Immediately After Local Femoral

Table 4: Model Summary

Model		Sum of Squares	df	Mean Square	F	Sig.
1	Regression	168.140	6	28.023	10.215	.000 b
	Residual	274.327	100	2.743		
	Total	442.467	106			

a. Dependent Variable: VAS Immediately After Local Femoral  
b. Predictors: (Constant), Thigh Circumference (cm), Ethnicity, Injection Type, Age, Gender BMI

Table 5: ANOVAa

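### Section 7 gives no alpha, testing order or exploratory label for the secondary and subgroup objectives, and the Results present a secondary outcome as the main finding without naming it as one

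*Combined protocol and SAP*

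**What the plan says.** The analysis plan in Section 7 is four sentences long. It opens with "Analyses will vary by specific aim", continues with "To evaluate our hypotheses, we will use exact and non-parametric hypothesis testing procedures" and "Confidence intervals (95%) of differences will be computed", and ends by allowing regression where adjustment is thought necessary. It does not list the hypotheses, and neither it nor any other section states an alpha, a test order, a multiplicity adjustment or an exploratory label.

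The primary objective is pain from the block itself (Section 1.6): "The primary objective is to measure the change in pain from a femoral or sciatic nerve block with the use of J-tip injected lidocaine". Section 1.7 then lists seven between-arm secondary objectives: infiltration pain, post-operative block efficacy, satisfaction, pain medication, nausea or vomiting, anti-emetic use and PACU time. An eighth looks for differences "with respect to BMI, thigh circumference, gender, ethnicity or operative time in pain reporting measures, satisfaction or medication usage". Section 3.2 repeats the seven and omits the eighth.

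Several of these outcomes are collected repeatedly. Section 3.2 has a "Home log of amount taken daily for post operative days one through three" for pain medication, and Section 4 says "The patient will record visual analogue pain scales on post-operative days one through three".

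In the Results, the regression text states that "Injection type statistically significantly predicts VAS immediately after local femoral", with a matching statement for the sciatic site. The scores immediately after the femoral and sciatic blocks appear only in the list of comparisons without statistical significance.

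**The concern.** The words primary and secondary rank the objectives, but nothing in the plan gives that ranking a consequence for testing or reporting. As written, a p-value below .05 on one post-operative day, one medication count or one subgroup could be reported in the same terms as a result on the primary, whatever the primary shows. A reader would have no rule for telling a confirmed effect from one of many looks.

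What is at stake is what the trial can be said to have shown. Its stated question is whether jet-injected lidocaine changes the pain of the nerve block. A reader who sees only the formal tests and regressions would take the trial as positive without learning that they answer a different, secondary question: the pain of giving the local anaesthetic.

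**Working it through.** **1. Figures in the document that can be reproduced.** No alpha, power or family-wise error rate is stated, so there is no planned figure to rebuild. The intervals in Table 2 of the Results can be checked from Table 1 (needle n = 54, J-Tip n = 57).

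- Femoral infiltration: SE = √(2.133²/54 + 1.524²/57) = 0.354; t = 2.030/0.354 ≈ 5.74; 95% interval 1.328 to 2.732, as printed in the unequal-variance row.
- Sciatic infiltration: SE = √(2.4553²/54 + 2.1631²/57) = 0.440; t = 2.228/0.440 ≈ 5.06; 95% interval about 1.355 to 3.101, as printed.

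The reported analysis therefore used two-sided 95% intervals. This supports two-sided 5% per test as a working assumption, though the plan does not say so.

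**2. How many tests?** Section 7 does not fix this, so two counts are carried.

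- One test per secondary objective: 7.
- Every site and day in Sections 3.2 and 4: infiltration VAS at two sites (2), VAS in PACU and on days 1 to 3 (4), patient and parent satisfaction (2), pain medication in PACU and on days 1 to 3 (4), nausea or vomiting (1), anti-emetics in PACU and on days 1 to 3 (4), PACU minutes (1). Total 18.

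Crossing five factors with three outcome domains would add 5 × 3 = 15, giving 33. This is an upper reading of a single bullet.

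**3. Chance of at least one false positive, all nulls true.** For k independent tests it is 1 − 0.95^k. For k = 7: 1 − 0.95^7 = 0.302. For k = 18: 1 − 0.95^18 = 0.603. For correlated tests, take Z_j = √ρ·U + √(1−ρ)·e_j, with U and e_j independent standard normal, and find the probability that any |Z_j| exceeds 1.96.

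| Tests | ρ = 0 | ρ = 0.5 | ρ = 0.9 |
|---|---|---|---|
| 7 | 30% | 23% | 11% |
| 18 | 60% | 40% | 15% |
| 33 | 82% | 53% | 18% |

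Even the lowest entry, 11%, is more than twice 5%.

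**4. Are the reported infiltration results at risk?** From the unequal-variance rows of Table 2, t = 5.741 on 95.525 df gives p ≈ 1.1e-7 (femoral), and t = 5.062 on 105.576 df gives p ≈ 1.8e-6 (sciatic). The Bonferroni limits are .05/7 = .0071, .05/18 = .0028 and .05/33 = .0015. Both results pass every one by a wide margin.

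**5. What the Results report.** There are 15 arm comparisons: 13 listed as not significant, plus the two infiltration scores. The 13 are six sedation variables, four VAS scores taken before an injection or block, the two block-pain scores and VAS before PACU discharge. So 3 of the 15 belong to the 18-test family, and 2 of the 15 are the primary. Those two have no difference, interval or p-value. The infiltration scores have stated hypotheses, t-tests, intervals and two regression models, and are nowhere called secondary.

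**The case against.** The strongest reply is that the inflation is hypothetical. The plan never says that each objective is tested at 5%, never ties its hypotheses to particular objectives, and never says that each day is a separate test. Sections 3.2 and 4 describe data collection. The objectives are ranked, the non-significant block-pain scores are disclosed, and the only significant arm differences are far too strong to be chance. The Results report no post-operative-day pain, satisfaction, tablet-count, nausea, anti-emetic or PACU-time comparison. They make no subgroup claim: the regressions contain main effects only and omit operative time.

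All of this is correct, and it limits the point. A reader might infer that a chance significant secondary or subgroup result is likely, or that the infiltration findings are themselves an artefact of multiple testing. The documents support neither. At correlation 0.5 the chance is 23% for seven tests and 40% for 18. It passes 50% only with 18 tests at low correlation or with the 33-test count. These rates also assume that no effect exists anywhere; without the two infiltration tests, the remaining 16 give 37% at correlation 0.5. Nor does the list of possible participant benefits in Section 10.2 amount to a rule for making claims.

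What the reply does not remove is the missing rule and the order of presentation. Disclosing the primary inside a list of 13 non-significant variables, without estimates, does not tell the reader that the trial's own primary comparison was not significant.

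**Conclusion.** The point holds as a gap in the plan with a visible effect on interpretation. On the assumption of two-sided 5% per test and all nulls true, the unaddressed family carries a false-positive chance of about 11% to 30% (one test per objective) or about 15% to 60% (18 tests), for correlations from 0.9 down to 0. The exact figure cannot be given because the plan does not fix the count. The 5% level is inferred, and the 18 tests are a reading of the collection schedule.

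The consequence in the Results is one of labelling. A secondary outcome carries all the formal inference, and the primary is mentioned only as not significant. It would go too far to say that a false finding has been reported, or that the plan prescribes unadjusted testing of every secondary.

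**What to change.** In Section 7, state that p-values for the secondary objectives are nominal and supportive. State also that the analyses by BMI, thigh circumference, gender, ethnicity and operative time are exploratory, reported as estimates with 95% intervals and without significance claims.

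In the Results, report the femoral and sciatic block-pain comparisons first, as the primary outcome, each with its difference and 95% interval, and say plainly that they were not significant. Then present infiltration VAS as a secondary, supportive outcome.

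Declare this labelling as post hoc. The results are known, so a gate or hierarchy added now cannot count as pre-specified. A formal gate would also need a pass rule across the two block sites, which the plan does not give. A Holm adjustment across the secondaries is optional; it would need one defined variable per objective, and the infiltration conclusion would not change.

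The cost is a few sentences and the reporting of estimates from scores already collected, with no new patients. The downside is that an isolated secondary or subgroup result below .05 can no longer be claimed as a confirmed J-Tip benefit.

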### **1.4 Sample Size**

A sample size of 50 per group, two groups, for a total of 100 patients is the goal. An additional 15 patients will be enrolled to account for withdrawals, bringing total enrolled to 115.

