## Results:

### Descriptive Statistics: Visual Analogy Scores (VAS) After Local Femoral and Local Sciatic Nerve Blocks

As seen in Table 1, the mean VAS immediately after local femoral for is 1.54 with a standard deviation 1.524 and the mean VAS immediately after local femoral for Needle Injections is 3.57 with a standard deviation 2.133. The mean VAS immediately after local femoral for J-Tip injections is 2.03 less than the mean VAS immediately after local femoral for Needle Injections. The difference time shows a large time gap and variation between the two injection types.

As seen in Table 1, the mean VAS immediately after local sciatic for is 2.272 with a standard deviation 2.1631 and the mean VAS immediately after local sciatic for Needle Injections is 4.5 with a standard deviation 2.4553. The mean VAS immediately after local sciatic for J-Tip injections is 2.228 less than the mean VAS immediately after local sciatic for Needle Injections. The difference time shows a large time gap and variation between the two injection types.

	Injection Type	N	Mean	Standard Deviation	Standard Error Mean
VAS Immediately After Local Femoral	Needle	54	3.57	2.133	.290
	J-Tip	57	1.54	1.524	.202
VAS Immediately After Local Sciatic	Needle	54	4.500	2.4553	.3341
	J-Tip	57	2.272	2.1631	.2865

Table 1: Group Statistics

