### Two-Sample T Test: Visual Analogy Scores (VAS) After Local Femoral and Local Sciatic Nerve Blocks

#### VAS Immediately After Local Femoral:

$H_0$  : No statistically significant difference exists between the mean of the VAS Immediately After Local Femoral for Needle Injections and the mean of VAS Immediately After Local Femoral in the J-Tip Injections.

$H_a$ : A statistically significant difference exists between the mean of the VAS Immediately After Local Femoral for Needle Injections and the mean of VAS Immediately After Local Femoral in the J-Tip Injections.

The VAS Immediately After Local Femoral for J-Tip Injections exceeds the mean VAS Immediately After Local Femoral for Needle Injections to a statistically significant degree,  $t(95.525) = 5.792$ ,  $p < .01$ , CI [1.328, 2.732], as indicated within Table 2.

VAS Immediately After Local Sciatic:

$H_0$  : No statistically significant difference exists between the mean of the VAS Immediately After Local Sciatic for Needle Injections and the mean of VAS Immediately After Local Sciatic in the J-Tip Injections.

$H_a$ : A statistically significant difference exists between the mean of the VAS Immediately After Local Sciatic for Needle Injections and the mean of VAS Immediately After Local Sciatic in the J-Tip Injections.

The VAS Immediately After Local Sciatic for J-Tip Injections exceeds the mean VAS Immediately After Local Sciatic for Needle Injections to a statistically significant degree,  $t(109) = 5.080$ ,  $p < .01$ ,  $[1.3587, 3.0974]$ , as indicated within Table 2.

		T-Test For Equality of Means							95% Confidence Interval of the Difference	
		F	Significance	t	df	Significance (2-tailed)	Mean Difference	Standard Error Difference		
VAS Immediately After Local Femoral	Equal Variances Assumed	4.491	.036	5.792	109	.000	2.030	.351	1.336	2.725
	Equal Variances Not Assumed			5.741	95.525	.000	2.030	.354	1.328	2.732
VAS Immediately After Local	Equal Variances Assumed	.515	.474	5.080	109	.000	2.2281	.4386	1.3587	3.0974

Sciatic	Equal Variances Not Assumed			5.062	105.576	.000	2.2281	.4401	1.3554	3.1007
---------	--	--	--	-------	---------	------	--------	-------	--------	--------

Table 2: Independent Samples Test

Ordinary Least Squares Regression: Visual Analogy Scores (VAS) After Local Femoral and Local Sciatic Nerve Blocks

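### Section 7 promises exact and non-parametric tests with 95% intervals, but the results use t-tests and mean comparisons without explanation and give the primary block pain scores no estimate

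*Combined protocol and SAP*

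**What the plan says.** Section 7 (Statistical Analysis Plan) contains three commitments:

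- On testing: "we will use exact and non-parametric hypothesis testing procedures". No test is named for any endpoint.
- On estimation: "Confidence intervals (95%) of differences will be computed".
- On adjustment: "Regression analysis will be employed when adjustment between comparison groups is considered necessary". No model type is named.

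Sections 1.6 and 3.1 make pain from the femoral or sciatic nerve block the primary objective. Pain from the local-anesthetic infiltration is secondary (Sections 1.7 and 3.2).

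The Results section shows three kinds of analysis:

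- The two infiltration VAS scores are compared by two-sample t-test; the main heading of Table 2 is "T-Test For Equality of Means".
- A list of 13 other variables is covered by one sentence, which begins "No statistical significance when comparing means Injection Type the following variables".
- The two infiltration scores are also analysed by OLS. The text for each model states: "The assumptions of linearity, independence of errors, homoscedasticity, unusual points, and normality of residuals were met".

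**The concern.** The plan fixes one family of tests, and nothing in the supplied results belongs to it. No exact or rank test appears, and no reason is given for using t-tests and mean comparisons instead.

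This matters most for the primary objective. VAS immediately after the femoral block and immediately after the sciatic block appear only in the list of 13. They have no named test, estimate, p-value or 95% interval. A reader cannot tell whether the data exclude a worthwhile difference in block pain or are merely inconclusive, and the planned analysis that would answer this is not shown.

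The same list includes the first, second and third type of sedation. These are drug categories, for which a mean has no meaning; an exact test of the kind planned would suit them.

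A separate, smaller problem is that the femoral OLS text declares equal variances while Table 2 points the other way for the same score.

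**Working it through.** **1. Plan against results**

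| Variable | Section 7 | Results |
|---|---|---|
| VAS after local infiltration (2) | exact or non-parametric test, 95% CI | t-test, 95% CI of the mean difference |
| VAS after femoral and sciatic block (2; primary) | same | in the list of 13; no estimate, p-value or CI |
| VAS before PACU discharge (1) | same | in the list of 13 |
| VAS before an infiltration or block (4) | same | in the list of 13 |
| Sedation type (3) and quantity (3) | same | in the list of 13; means compared |
| Adjusted infiltration VAS (2) | regression allowed | OLS |

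The list adds up: 2 + 1 + 4 + 6 = 13. Three of the 13 are pain outcomes measured after a procedure.

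**2. Reproducing Table 2 from Table 1**

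Femoral inputs: needle n = 54, mean 3.57, SD 2.133; J-Tip n = 57, mean 1.54, SD 1.524. Difference 3.57 − 1.54 = 2.03.

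- Pooled variance = (53 × 2.133² + 56 × 1.524²)/109 = 3.405. SE = √3.405 × √(1/54 + 1/57) = .350. t = 2.03/.350 = 5.79 on 109 df (printed 5.792).
- Welch SE = √(2.133²/54 + 1.524²/57) = .354. t = 5.74 on 95.5 df, 95% CI 1.328 to 2.732 (printed 5.741, 95.525, and the same CI).

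Sciatic inputs: needle mean 4.500, SD 2.4553; J-Tip mean 2.272, SD 2.1631. Pooled t = 5.08, 95% CI 1.359 to 3.097 (printed 5.080, 1.3587 to 3.0974).

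Table 2 is reproduced. The femoral text, however, pairs the pooled t (5.792) with the Welch df (95.525).

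**3. Equal variances**

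- Femoral: variance ratio (2.133/1.524)² = 1.96. The printed F of 4.491 on (1, 109) df gives p = .036. The investigators report the unequal-variance df and CI, yet the OLS text declares homoscedasticity met.
- Sciatic: variance ratio (2.4553/2.1631)² = 1.29. The printed F of .515 gives p = .474. There is no conflict.
- Practical size: the femoral SE moves from .350 to .354, about 1%.

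**4. Would a rank test change the infiltration findings?**

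There are no patient-level data, so the planned p-values cannot be computed. As an illustration, assume gamma-shaped scores with the Table 1 means and SDs, rounded and clipped to 0–10. In 2,000 simulated trials Mann-Whitney gave p < .05 in 100% of femoral runs and 99.95% of sciatic runs.

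**5. Would it change the block result?**

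This cannot be determined. No mean, SD or distribution is printed for block VAS. Under assumed gamma-shaped scores with 54 against 57 children, the share of trials in which the rank test and the t-test disagree at 5% depends on where scores sit on the scale:

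- true difference 0.7 to 0.9, J-Tip mean 1.6 to 2.5: about 11% to 18%;
- true difference 0.7 to 0.9, base mean 4: about 6% to 7%;
- true difference 0.7 to 0.9, base mean 5.5: about 4%;
- no true difference, base mean 4 or 5.5: about 2% to 3%.

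The rank test is usually, but not always, the more powerful at low means; at 5.5 the two have equal power.

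**The case against.** The strongest reply is that little turns on this. The infiltration t statistics exceed 5, the arms are nearly equal in size, and the variance issue barely moves the standard error. The Results are also visibly incomplete: there is no Table 6, an appendix is cited but not supplied, and the sentence on the 13 variables names no test. All of this stands. It limits the consequence for infiltration pain, but does not explain the departure or supply the missing block estimates.

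Several stronger readings are tempting, and the documents do not support them:

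- *Every analysis breaches the plan.* Section 7 allows regression and names no model, so OLS is not a breach.
- *The assumptions sentence is offered to justify all the results, and the tables refute it.* The sentence is attached only to the two OLS models. Table 2 conflicts with it for the femoral score alone. Even there the evidence is indirect: the equal-variance test uses raw scores from 111 children, whereas the sentence concerns a six-predictor model fitted to 107 (total df 106), for which no residual diagnostics are shown.
- *The null block result is an artefact of scores piled at zero.* J-Tip infiltration means lie only about 1 SD above zero (1.54/1.524 = 1.01; 2.272/2.1631 = 1.05). A normal curve would put 15.6% and 14.7% of scores below the scale minimum, so skew is likely there. But those are raw infiltration scores. Section 4 says pain usually arises when the block needle passes through the fascia, which is not anesthetized, so block scores may sit higher.
- *The tests were chosen after the data were seen.* Nothing in the documents says when they were chosen. An unexplained change leaves that question open, but does not answer it.
- *The femoral model is invalid because it can predict negative pain.* That takes a J-Tip child 2 SD above average on age, BMI and thigh circumference together. Two SD of age is about 3.2 years (SD 1.58, from Table 7: .193 × 2.043/.250) above an unprinted mean, in a trial limited to ages 11 to 17. Such a child may not be eligible.

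**Conclusion.** The point holds as an unexplained departure from the only testing rule in the plan. It matters chiefly because the primary block pain scores are reported without the planned analysis or the promised 95% intervals. Using means for sedation type is wrong whatever the distributions.

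The homoscedasticity statement needs correction for the femoral model only, and the effect of that issue on the standard error is about 1%. The infiltration conclusions would very probably survive a rank test; this rests on the assumed score shape in the simulation and on t statistics above 5.

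For block VAS, neither the direction nor the size of any change can be stated. The simulated disagreement of roughly 2% to 18% reflects assumptions about an unprinted distribution and is not an estimate for this trial. That what was supplied is the full set of results is also an assumption.

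**What to change.** On the existing data:

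1. For each between-arm VAS comparison, starting with VAS immediately after the femoral and sciatic blocks, report a rank test with a 95% CI of the difference. An exact or permutation Wilcoxon-Mann-Whitney test with the Hodges-Lehmann shift is one suitable choice. Section 7 names no specific test, so state which one is used.
2. Compare type of sedation with an exact test for categorical data.
3. Keep the t-tests as sensitivity analyses. For the femoral score, match the t value to its df.
4. State in the report that t-tests and mean comparisons departed from Section 7, and why.
5. For the femoral OLS, correct the homoscedasticity statement and use heteroscedasticity-robust standard errors. Proportional-odds regression with the same covariates is an optional addition; it carries its own assumption, which would need checking.

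The cost is a small re-run with no new data. The downside is that a shift estimate is slightly less familiar to readers than a mean difference.
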